This baseline visit will be performed at the start of Cycle 1 only. The initial dose of clomiphene citrate will be 100 mg/day, which may be adjusted upwards or downward depending on response in subsequent cycles. Women may undergo a total of up to 3 cycles culminating in hCG administration. Subjects may begin subsequent cycles immediately following failed cycles, as long as they meet baseline criteria of a negative urine pregnancy test. Subjects may continue in the study after one failed cycle (i.e. either no development of follicles on study medication). If a subject experiences a second failed cycle, it is recommended to discontinue the subject from the study.

1. Subject will call with menses and come in between days 1-5 of their menstrual cycle (Preferably day 3 for baseline monitoring visit).
2. Check Urine Pregnancy test.
3. Obtain weight.
4. Perform baseline ultrasound. If subject has a cyst with a mean diameter of >30mm, do not continue the visit. Have the subject return with her next menses for a repeat baseline visit.
5. Collect vaginal microbiome and rectal microbiome swab.
6. Dispense Infertility Treatment Study Medication (see Table 9). Please note, if the female has a prior history of over-response to clomiphene citrate at the 100mg dose, the starting dose may be adjusted downward.
7. Obtain central core lab specimens and blood and urine reserve (to be stored on site) for ancillary studies (with consent).

8. Dispense menstrual and intercourse diaries.
9. Schedule Day 8-12 visit for follicular monitoring.

Table 9: Study Medication and Dosing

Protocol	interval	dose	method	start	finish	future cycles
CC	Daily	100 mg	pill	Day 3*	Day 7	Can be started at 50-150 mg/d= (1 to 3 pills)

*(+/- 2 days)

Empirical treatment Cycle Visit number 2:

Within 3 days after completing 5-day drug cycle (Cycle Day 8-12)

1. Transvaginal ultrasound for endometrial and follicular monitoring.
2. Adverse effects and concomitant medications query.
3. During cycle 2 & 3, medication bottles and menstrual diaries from previous cycle will be collected.

Study treatment Cycle visits number 3 and beyond:

Visits for subjects will be conducted on an individualized basis until hCG administration. When a decision has been made to give hCG on the next day, a follow up monitoring visit on that day is unnecessary.

1. Transvaginal ultrasound examination for endometrial and follicular monitoring.
2. Adverse effects and concomitant medications query.

hCG administration day:

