1. Each site will perform its standard insemination procedure.
2. Record parameters of semen analysis before and after sperm preparation.
3. Record time of insemination.
4. During cycle 1 & 2, medication for the next cycle will be dispensed along with menstrual diaries. The subject will be instructed that this medication SHOULD NOT be started until the current cycle is completed, either pregnancy or no pregnancy has been confirmed with a pregnancy test and the subject has spoken with the site. The subject will be instructed to perform a urine pregnancy test (see below under Urine pregnancy test) two weeks after the insemination.

Urine Pregnancy test:

To be conducted 2 weeks after insemination at home or at start of menses.

Patient will perform a urine pregnancy test at home and call the site with the results. If the test is positive, the patient will be scheduled for a serum hCG test. If the urine pregnancy test is negative, and menses have begun, instructions will be provided to begin the next cycle. If the urine test is negative and menses has not begun, the subject should come in for a serum pregnancy test and the site should follow standard practice for a patient with no menses following IUI.

Serum hCG Visits:

To be conducted after + urine pregnancy test

1. Obtain blood sample for qHCG. If positive result, will schedule for repeat 2 days later.

Three possible outcomes:

- A. No pregnancy
- B. Positive test → retest for rising level in 2 days → no pregnancy
- C. Positive test → retest for rising level in 2 days → positive pregnancy

A. Negative Serum or Urine Pregnancy Test/No pregnancy

Repeat cycles until pregnancy occurs or treatment cycles conclude; women may receive hCG up to 3 times (cycles). There may be anticipated or unanticipated breaks in protocol due to medical necessity, patient request or due to site holiday recess, but none of the breaks should exceed approximately 4 weeks (allowing the subject approximately 16 weeks to complete Phase 2 of the protocol).

Criteria to initiate Cycles 2 or 3 (Menstrual Cycle Day 3 +/- 2 days):

1. Negative urine pregnancy test (within 2 days)

B. Positive Pregnancy Test (no pregnancy)

Patient will return in 2 days to check for a rising level in serum β hCG; if there is not a rising level, patient will initiate Cycles 2, or 3 (see above)

C. Positive Pregnancy Test (pregnancy)

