8.1.3 Expected Serious Adverse Events

We do not anticipate serious adverse events during the first phase of this trial with lifestyle modification. These are more likely during the second and third phases of the trial. The expected serious adverse events are likely related to ovarian cyst formation which can result in hospitalization or surgery. Pregnancy and especially multiple pregnancy may also be a source of ectopic pregnancy, prematurity and maternal complications such as pre-eclampsia or eclampsia requiring hospital admission and induction of labor. None of the drugs or interventions are associated with increased risk of congenital anomalies.

9 Criteria for Modification or Discontinuation of Study Interventions

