11.3.6 Establishment of Pregnancy Registry

We intend to establish a pregnancy registry for this trial to establish outcomes of pregnancy. Couples who conceive will be offered participation in the Pregnancy Registry and a separate informed consent form will be obtained if they choose to participate. We will track the outcomes of all randomized subjects who have a positive serum pregnancy screen during the course of this study. We will record biochemical pregnancies (defined as positive serum pregnancy screens without ultrasonically detected pregnancies), ectopic pregnancies, and all intrauterine pregnancy losses both before and after 20 weeks including missed abortions, spontaneous abortions, elective abortions, fetal demises, and stillbirths. We will review pregnancy and birth records of the mother and of the fetus to establish neonatal morbidity and mortality and the presence of fetal anomalies. This will be done for all subjects who conceive.

If they participate in the Pregnancy Registry, we will extract from these records concomitant medical and obstetrical conditions, exposure information on all other medical products used, including prescription products, over-the-counter (OTC) products, dietary supplements, vaccines, and insertable or implantable medical devices. We will file individual case reports for all congenital anomalies which will be considered a serious adverse event. Additionally we will provide to the FDA a written annual status report of the pregnancy registry as specified in the guidelines above. We intend at a minimum to perform an annual parent directed screening questionnaire to assess the infant's developmental milestones for the first three years after birth as recommended by the FDA and to review the child's CDC growth curve and medical records. The registry will follow children until age 3. A survey will be administered to the mother annually that will screen for cognitive, and neurodevelopment up to age 3. If medical issues arise from the survey, a medical record review will be performed for more extensive assessment.

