11.4 Adverse Event Reporting

11.4.1 Serious Adverse Events

All serious adverse events (SAEs) that occur from randomization at Phase I through thirty days after the last dose of study medication (orlistat, clomiphene, or hCG) must be reported or if the patient is pregnant, 6 weeks following delivery. A serious adverse event is defined as: fatal or immediately life-threatening; severely or permanently disabling; requiring or prolonging inpatient hospitalization; overdose (intentional or accidental); congenital anomaly; pregnancy loss after 20 weeks gestation; neonatal death up to 6 weeks after delivery; or, any event adversely affecting the study's risk/benefit ratio. Additionally, any event that, based on appropriate medical judgment, may jeopardize the subject's health and may require medical or surgical intervention to prevent one of the outcomes listed above is considered an SAE.

If an SAE occurs and is thought to be related to the study medication, the study medication will be discontinued.

The site PI will report the SAE by completing and signing the Serious Adverse Event Report Form [available in the "Study Forms" section of the RMN members-only website], and then emailing the document in PDF format to [contact]. Subjects will be identified by study number only. No other identifying information will be included on the form. The site PI must

determine and record on the SAE form whether the SAE is unanticipated or anticipated, and if it is related, possibly related, or unrelated to participation in the research.

DCC staff will enter the SAE information in the central database. The Safety Surveillance team, consisting of the DCC, NICHD research scientist and lead PI of the protocol, will analyze the SAE to determine if it meets the criteria listed in the OHRP 45CFR46 and/or FDA 21CFR312.32 & 3.14.80.

These determinations will dictate timeframes for sites' submission to the DCC, and the DCC's submission to the DSMB (**Table 12**):

[figure not shown]
Table 12: Types of Serious Adverse Events and their reporting requirements

TYPE	SITE	DCC
Unanticipated and related/possibly related SAE, fatal or life-threatening	Report to DCC within 1 business day of discovery	Notify DSMB by end of next business day of receiving site report
Other unanticipated and related/possibly related SAE	Report to DCC within 1 business day of discovery	Notify DSMB 5 business days of receiving site report

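### The protocol contradicts itself on a positive serum hCG that does not rise: whether it counts as a pregnancy, whether a scan follows, and which SAE window applies

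*Combined protocol and SAP*

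**What the plan says.** Section 7.2 (Serum hCG Visits) lists three outcomes. The second is "Positive test → retest for rising level in 2 days → no pregnancy". Its paragraph is headed "B. Positive Pregnancy Test (no pregnancy" and gives one action: "if there is not a rising level, patient will initiate Cycles 2, or 3 (see above". The cross-reference leads to the criterion for starting Cycle 2 or 3, "Negative urine pregnancy test (within 2 days", at menstrual cycle day 3 plus or minus 2. The text on the Phase 2 baseline visit repeats it: later cycles may follow "as long as they meet baseline criteria of a negative urine pregnancy test".

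The step that schedules the pregnancy ultrasound is listed under outcome C, the rising level. Section 7.2 also makes a rise part of its definition of biochemical pregnancy. The footnote to Table 7 (section 7.1) differs: it times an obstetric ultrasound at 14 to 21 days from the positive result and sets no condition of a rise.

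Section 11.3.6 states: "We will track the outcomes of all randomized subjects who have a positive serum pregnancy screen during the course of this study". Its definition of biochemical pregnancy is a positive serum screen with nothing detected on ultrasound, again with no rise required. It also says that ectopic pregnancies will be recorded.

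Section 11.4.1 runs SAE reporting "through thirty days after the last dose of study medication (orlistat, clomiphene, or hCG) must be reported or if the patient is pregnant", in which case it extends to six weeks after delivery. Section 8.1.3 names the event at issue among the expected SAEs: "Pregnancy and especially multiple pregnancy may also be a source of ectopic pregnancy". Sections 1.7 and 10.3.2 include ectopics and pregnancies of unknown location (PULs) in the secondary outcome of pregnancy loss.

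**The concern.** The same woman is not pregnant under one section and a tracked pregnancy under another. Three things depend on which section a site follows: how she is counted in the pregnancy-loss outcome, whether an obstetric scan is scheduled, and how long her SAEs are reported.

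The gap is sharpest after the third cycle. Outcome B sends her only to Cycle 2 or 3, so a third-cycle woman has no written path. The end-of-Phase-2 visit is timed for women who are pregnant, for women whose third-cycle test is negative, and for withdrawals. She fits none of these clearly.

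At stake is a safety-relevant secondary outcome. The trial is open label, and sites would be choosing between conflicting definitions when they classify ectopics, PULs and biochemical losses.

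**Working it through.** The plan gives no figure on this point to reproduce. The check has two parts: the sections set side by side, and a day count from the stated timings.

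**Sections side by side**

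| Question | One reading | The other reading |
|---|---|---|
| Is a positive, non-rising hCG a pregnancy? | No: 7.2 outcome B; 7.2 requires a rise even for biochemical pregnancy | Yes: 11.3.6 requires no rise and tracks every positive serum screen |
| Is an obstetric scan scheduled? | Only after a rise: 7.2, listed under outcome C | After any positive result: Table 7 footnote |
| Which SAE window applies? | 30 days after last dose, if not pregnant: 11.4.1 | To 6 weeks after delivery, if pregnant: 11.4.1 |

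Section 11.4.1 does not say which row-three reading covers these women. It also gives no end date for a pregnancy that ends without a delivery, which is the case for an ectopic or an early loss.

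**Day count from the hCG trigger (day 0)**

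Inputs from section 7.2: insemination within 44 hours of the trigger; urine test 2 weeks later; repeat serum test 2 days after the first. Assumptions: insemination at 44 hours, and the first serum test on the day of the urine test.

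- Insemination: 44/24 = day 1.8
- First serum test: 1.8 + 14 = day 15.8
- Repeat serum test: 15.8 + 2 = day 17.8, about day 18
- Scan under the Table 7 footnote: 15.8 + 14 = day 29.8 to 15.8 + 21 = day 36.8, about day 30 to 37

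*After Cycle 3, if she is treated as not pregnant.* The last dose is the hCG trigger, so SAE reporting ends on day 30. Time left after the repeat: 30 − 17.8 = 12.2 days. If the first serum test is 3 days later, the repeat is on day 20.8, leaving 30 − 20.8 = 9.2 days, and the scan falls at about day 33 to 40. In both cases the scan falls at or after the end of SAE reporting.

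*After Cycle 1 or 2.* Suppose the next cycle begins 0 to 14 days after the repeat (assumed range). Clomiphene ends on cycle day 5 to 9 (Table 9: day 7, with the start allowed plus or minus 2 days).

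- Earliest last clomiphene dose: 17.8 + 0 + (5 − 1) = day 21.8; SAE reporting to 21.8 + 30 = day 51.8
- Latest last clomiphene dose: 17.8 + 14 + (9 − 1) = day 39.8; SAE reporting to 39.8 + 30 = day 69.8

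So the window restarts and runs to about day 52 to 70, or longer once hCG is given again. The shortened window is a Cycle 3 problem only.

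**The case against.** Read alone, outcome B might lead a reader to infer that these women are neither imaged nor followed. The documents as a whole do not support that. The Table 7 footnote ties a scan to any positive result, and section 11.3.6 commits to tracking every positive serum screen. This objection stands. What remains is that section 7.2 says something different, and the plan does not state which section prevails.

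There are also safeguards before another cycle. Sections 7.2 and 7.3.3 provide for these:

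- a negative urine test
- a cycle-day requirement
- an instruction not to start the next cycle's medication until pregnancy status has been settled by a test and the woman has spoken with the site
- allowance for breaks on medical grounds
- a transvaginal scan with an adverse-effects query on cycle days 8 to 12

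These points stand for Cycles 1 and 2. However, a urine test does not locate a pregnancy, the day 8 to 12 scan is ordered for endometrium and follicles, and none of these steps applies after Cycle 3.

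A reader might also infer that the SAE window closes for every such woman. It does not. After Cycles 1 and 2 a new dose restarts it. Section 11.4.1 also never adopts outcome B's label, and a woman with an ectopic is pregnant in the ordinary sense. After Cycle 3 the end-of-Phase-2 visit, if it is held, includes an adverse-event query and repeat serum tests. The Cycle 3 gap is therefore a matter of wording that permits a short window. The plan does not state that the window closes.

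Finally, both arms follow the same pathway. The documents give no basis for saying that any undercount would differ between arms.

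**Conclusion.** The contradiction is real and should be corrected. Sections 7.1, 7.2, 11.3.6 and 11.4.1 disagree, or are silent, on pregnancy status, scan and SAE window for a positive, non-rising serum hCG. Two consequences follow: pregnancy loss including ectopics and PULs can be classified inconsistently, and an ectopic recognised late after Cycle 3 can fall outside SAE reporting. The second depends on the site treating the woman as not pregnant. In that case about 12 days of reporting remain after the repeat test (about 9 if the serum test is 3 days later), given insemination at 44 hours.

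The primary outcome does not depend on how this branch is labelled, and the sample size is untouched.

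A reader might be tempted to estimate the number of ectopics missed. The documents do not support such a count. The OWL PCOS data show 1 surgical ectopic (Table 5) among 8 + 16 + 14 = 38 conceptions (Table 3), or 2.6%, with an exact 95% interval of 0.07% to 13.8%. That is a different population, and nothing in the plan says what share of ectopics would show a non-rising repeat.

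**What to change.** Reconcile the Table 7 footnote, section 7.2 (outcomes B and C and the definition of biochemical pregnancy), section 11.3.6 and section 11.4.1.

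- For outcome classification and SAE reporting, apply the section 11.3.6 rule: any positive serum hCG is tracked until its outcome is documented.
- Record outcome B as biochemical loss, ectopic or PUL in place of the present label, and use one definition of biochemical pregnancy throughout.
- State in section 11.4.1 which SAE window applies to these women, including after Cycle 3, and when it ends for a pregnancy without a delivery.

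The passages on imaging, clinical follow-up and the timing of any further cycle must also be made consistent. What they should require is for the sponsor and sites to settle.

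The cost is protocol wording and one outcome field.

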7.3 Special Instructions and Definitions of Evaluations

7.3.1 History and Demographics

[figure not shown]
Medical history, including infertility treatment history, and concomitant medicines will be obtained using standardized procedures and case report forms (CRFs) developed by the RMN.

7.3.2 Physical Exam

A physical exam with a standard pelvic and breast exam will be performed on all patients by a study physician. Height, weight and waist and hip circumferences will be recorded to the nearest 0.1 cm, 0.1 kg and 1 cm, respectively. Waist will be measured at the level of the umbilicus and hip circumference will be measured at the widest diameter. Participants will be weighed while dressed in light clothing, without shoes. Weight and waist circumference will be collected at each site visit. Blood pressure will be determined in the right arm in the sitting position, and a large cuff will be used as necessary. Blood pressure will be assessed at each visit. Elevated blood pressures ($\geq 160/100$) will be repeated following acclimation to the study environment. All patients aged 21 and older should have had a normal Pap smear in accordance with current ACOG guidelines⁸⁰; otherwise, one should be performed at the screening exam. Subjects with cytological abnormalities will need to have these resolved prior to study entry.

A hirsutism assessment will be made via the modified Ferriman-Gallwey hirsutism score (**Figure 4**) by trained study personnel⁸¹.

Figure 4: Modified Ferriman-Gallwey Hirsutism Scale

Medscape

An acne assessment will be made by trained personnel using a standard acne lesion assessment (count) diagram and definitions (**Table 10**). Photographic examples of each grade will be provided to investigators as well as training to study personnel. When counting facial acne lesions, it is important that all lesions be counted, both non-inflammatory and inflammatory, examining areas of the forehead, cheeks, and chin and avoiding the nose.

Table 10: Acne Grading Method

Name	Description
Open Comedone (Blackhead)	Results when residual skin oil, makeup, dirt, dead skin, and small hairs impact a sebaceous follicle and prevent the pore from functioning correctly. If the pore is open, the comedone will be dark in appearance and is thus called a blackhead.

Closed Comedone (Whitehead)	Non-inflammatory comedone with a white center.
Papule	An inflammatory comedone that resembles a small red bump on the skin.
Pustule	An active infection of the skin that consists of dead skin cells and bacteria. These lesions are spherical in appearance and are filled with pus. Often reddish in color, pustules may be painful and will break open easily if scratched or bumped.
Nodule	A natural progression of a papule. They appear very similar to papules, but are inflamed and penetrate deep into the skin. They are often very painful.

7.3.3 Ultrasound and Imaging Exams

An ultrasound exam will be performed with a transvaginal probe. The following measures will be obtained: uterine dimensions, leiomyoma presence size and location, other uterine abnormalities (Mullerian or vascular), endometrial thickness, ovarian size in three dimensions, the size of the largest ovarian follicle, antral follicle count in each ovary (complete ovary) and ovarian morphology. Endometrial thickness is the largest anterior-posterior measurement of the endometrium in the sagittal plane. Ovarian size is determined by measuring the largest plane of the ovary in two dimensions and then turning the vaginal probe 90 degrees and obtaining a third measurement. Ovarian volume is determined by the formula for a prolate ellipsoid (length x width x height x $\pi/6$)⁸². This same ultrasound will be performed at each subsequent ultrasound visit (including follicular monitoring visits during Phase II). If the patient has had no prior test of tubal patency, this may be the desired time to perform a sonohysterogram to determine tubal patency.

7.3.4 Biospecimens

Serum: A phlebotomy will be performed at the appropriate visit. Blood will be obtained in the appropriate tubes for specimen processing and eventual aliquoting. If a subject has been fasting, this will be the first order of the study visit agenda, and subjects will be given an appropriate snack or drink after to ease hunger.

Blood for DNA: Whole blood will be collected (if consented) in an EDTA tube for eventual extraction of DNA from WBCs. This will be frozen after collection.

Urine: A urine specimen will be obtained at the visit and aliquoted into the appropriate storage units.

Stool Microbiome: During a pelvic exam, a Dacron swab will be used to sample the rectum and placed in a NAT (Nucleic Acid Transport) collection tube. After collection, the samples will be refrigerated until processing. This collection method will allow for DNA analysis of the stool microbiome.

Vaginal Microbiome: During a pelvic exam with speculum in place in the vagina, Two Dacron swabs will be used to sample the posterior fornix and cervix and placed in a NAT (Nucleic Acid Transport, CentraCare Laboratory Services, St. Cloud, MN) collection tube. After collection the samples will be refrigerated until processing to preserve the DNA material from degradation. This collection method will allow for DNA analysis of the vaginal microbiome.

Salivary Analytes: A salivary collection kit will be used (SalivaBio Oral Swab (SOS)). This will be dispensed on the visit prior to the collection visit. A swab will be collected and placed in the collection tube for preservation and processing according to standard operating procedures (<https://www.salimetrics.com/collection-systems>). This will be collected at home at 9pm on the evening before the visit, and at 9am the day of the visit (in clinic if an am visit). The goal is to measure biomarkers for stress at the respective peak and nadir of the diurnal cycle.

Biospecimen Disposition: Specimens obtained under consent for the FIT-PLESE study will be aliquoted for storage at the study site, shipment to the RMN Central Core Laboratories, or shipment to the RMN Biologic Repository. Additionally subjects will be offered the possibility to sign a separate consent to participate in our Registry Protocol, and will contribute additional specimens as indicated by that protocol. Further details of specimen processing can be found in the Manual of Operations and Procedures.

